4.8. Monitoring Participant Laboratory Values and Subsequent Dose Adjustments

In addition to the algorithms designed for safety monitoring in this trial, an additional safety feature of CIRT is that when certain laboratory thresholds are crossed, the physician responsible for the subject will be notified.

The specific thresholds for drug discontinuation, re-initiation, down-titration, and up-titration are described in detail in the trial algorithms that will be used to monitor safety and make dose changes across the study on a central and consistent basis. No increase in weekly dose will occur unless all of the following criterion are met: the WBC count is $\geq 3,500/\text{ul}$, the platelet count is $\geq 75,000/\text{ul}$, the CrCl is $\geq 40\text{ml}/\text{min}$, ALT/AST levels are $\leq 1.5\times$ ULN, hematocrit is ≥ 27 percent, and there are no clinically important symptoms (defined as stomatitis, diarrhea, vomiting, or cough either productive of sputum or associated with a fever or with severe shortness of breath). As also described in the study algorithms, a reduction in dose will occur if

there are changes in some of these parameters that may suggest early toxicity but that are not severe enough to warrant drug discontinuation. For example, for a subject taking 20 mg of the study drug, while a drop in the platelet count below 50,000 will lead to temporary drug discontinuation, a reduction below 75,000 but above 50,000 would lead to a 5 mg decrease in the current weekly dosing. After clinical resolution of any events that lead to drug discontinuation and after a return of all laboratory abnormalities to a safe range, study drug will be re-initiated and up-titrated over time in 5 mg increments back toward the maximal target dose of 20 mg po weekly, as tolerated. Responsible physicians will be informed of any changes in study drug dosing recommended by the clinical coordinating center. Adverse events, patient symptoms, laboratory abnormalities, or other reasons for discontinuation of or reduction in dose of study drug will be collected through case report forms and monitored centrally by the Data Coordinating Center (DCC).

4.9. Monitoring Participant Symptoms and Subsequent Dose Adjustments

Participants will have regularly scheduled visits with the local investigator during which the study staff will carefully assess the patients for any signs or symptoms of drug toxicity, in addition to the occurrence of any trial endpoints. A questionnaire designed to capture information about drug toxicity (including symptoms of a pulmonary, infectious, gastrointestinal, hematologic, dermatologic, and other toxicities), intercurrent hospitalizations, and elective or planned surgical procedures will be administered to all study participants at the time of regularly scheduled safety lab draws (once a month for the first 6 months after randomization, then at least bi-monthly).

The questionnaire will be administered both by local study staff via the telephone or in person. Study algorithms will combine data from recent laboratory safety evaluations with patient reported symptoms to determine study drug dosing and/or cessation, including sham placebo dose adjustments. Responsible physicians will be informed of any changes in the study medication dosing. As noted above, adverse events, patient symptoms, laboratory abnormalities, or other reasons for discontinuation of or reduction in dose of study drug will be collected through case report forms and monitored centrally by the Data Coordinating Center (DCC).

Study coordinators are given instructions to contact the Medical Monitor for symptoms or signs that raise the possibility of drug toxicity, including the development of new clinically significant effusions or ascites. As noted above, in order to better understand the toxicities of methotrexate, at 6 months a blood sample will be collected from all participants for the measurement of key metabolites of methotrexate. Furthermore, if requested by the DSMB, aggregate data on adverse events, stratified by blinded treatment group, will be reviewed on a quarterly basis by the Chair of the DSMB, who may then request a more detailed analysis and/or forward the data to the full Board.

4.10. Medical Monitor

A Medical Monitor will be on call 24 hours a day 7 days each week. A senior board-certified rheumatologist with expertise in drug safety (Senior Rheumatologist) will supervise the Monitors. The Monitors will be rheumatologists (fellows or junior faculty) who will be trained by the Senior Rheumatologist and will be accessible via pager. The Monitors will be referred subjects based on the pre-laboratory questionnaire or laboratory abnormalities and will have access to the subjects' laboratory data and clinical information via the EDC system. The Monitors will have the option of unblinding the treatment allocation of a subject, if the symptoms and acuity of illness make doing so warranted.

Monitors will help sites determine whether the symptoms being described by patients are concerning, whether interruptions in study drug are warranted, and whether re-initiating study drug is safe. While all Monitors will have experience with methotrexate prescribing, the Senior Rheumatologist will compile a list of scenarios as they occur that will allow the Monitors to have a consistent approach. The Monitors as a group will meet monthly with the Senior Rheumatologist to discuss these scenarios. As the trial progresses, these meetings are anticipated to occur every quarter.

4.11. Endpoint Definitions and Documentation

The primary endpoint is defined as the time to the first adjudication committee confirmed major adverse cardiovascular event (MACE) occurring during the double-blind treatment period, which is a composite of CV death, non-fatal MI, and stroke.

An independent Clinical Endpoints Committee (CEC) will review and adjudicate all clinical events that constitute the primary composite endpoint (CV deaths, non-fatal MI, and stroke). In addition, the CEC will adjudicate a number of secondary endpoints, including all deaths, all hospitalizations for unstable angina requiring unplanned revascularization, all hospitalizations for congestive heart failure, and all arterial revascularization procedures. The CEC will be blinded to treatment assignment. Formal definitions for the individual components of the primary endpoint, hospitalization for unstable angina requiring unplanned revascularization, hospitalizations for congestive heart failure, and arterial revascularization are provided in the Clinical Endpoint Committee (CEC) Charter. The secondary and tertiary endpoints listed in sections 2.2 and 2.3 not adjudicated by the CEC will be validated by non-CEC staff. For example, incident diabetes will be confirmed by a combination of patient or physician report, new anti-diabetic medications, or by protocol-based measures of glucose and HbA1c performed at least twice annually. Incident venous thromboembolism will be confirmed using documentation of imaging studies including a venous ultrasound or venogram showing deep venous thrombosis or a pulmonary arteriogram, CT scan, or ventilation-perfusion scan showing pulmonary embolism.

Other non-adjudicated clinical events of interest include microvascular disease (nephropathy and retinopathy), sleep apnea, and age-related macular degeneration.

Full descriptions of the methods for endpoint ascertainment and the specific definitions of each adjudicated trial endpoint are contained in the Clinical Endpoint Charter (CEC).

4.12. Procedures for Emergency Unblinding

As part of the trial monitoring structure, a medical monitor will also be available on a 24 hour basis who has the ability to electronically access individual patient data files should unblinding be needed. All of these instances will be tracked within the EDC system.

4.13. Investigator Education Programs

To ensure that all investigators and study coordinators are comfortable with LDM regardless of specialty area, a face-to-face targeted education program will be provided as part of the trial Investigator Meetings and a series of on-line teleconference/webinars will be provided every 6 months where educational information regarding LDM will be updated and reinforced.

4.14. Drug Compliance Monitoring

The primary measure of compliance will be based on the return of calendar packs to the physician at each of the 4-month office visits (at which time new calendar packs will be issued as long as no trial endpoint or major side-effects have occurred).

As an additional measure of compliance, washed packed red blood cells collected 6 months after randomization will be stored in a central laboratory for measures of methotrexate levels. This will be done using a methotrexate polyglutamate assay that provides a semi-quantitative method of evaluating methotrexate absorption and metabolism. The results of this assay will not be available to blinded study staff until after the study has completed and the database has been locked.

4.15. Central Laboratory and Bio-bank

Blood samples for storage in a bio-bank at Brigham and Women's Hospital will be obtained at the pre-run-in, randomization, and at 8 and 24 months after randomization. Processing and long-term storage of these samples will be done in a liquid nitrogen biobank facility in Boston, which has been used for this purpose in multiple prior NIH-funded trials and large cohort studies. White blood cells from the pre-run-in sample will also be stored in this facility to allow for DNA extraction at a later date. As described in the informed consent documents, participation in the genetic bio-banking portions of CIRT will be on an "opt-out" basis and are not a requirement for participation in the main trial.

4.16. Serious Adverse Events (SAEs)

All subjects will be monitored at the local study sites on a regular basis during the course of study involvement. All SAEs will be reported within 24 hours of local event awareness (but no later than the next business day) to the Data Coordinating Center (DCC). Initial reports will often not be complete. Central study staff will guide the site regarding the completion of a SAE form along with retrieval of the pertinent medical records for determination of a final diagnosis. An updated full written report will be filed as additional information becomes available within 10 working days (14 calendar days). The report will include a complete description of the event, use of all concomitant medications, and the local investigator's assessment of causality of the SAE to study therapy. All serious adverse events will be recorded in the core study database within 1 week of report by the local study site personnel. SAE reporting for all subjects will occur in accordance with the central institutional review board (IRB) requirements. Study staff may contact patients directly to determine the resolution of adverse events.

4.17. Data Coordination and Treatment Masking

The DCC is responsible for the facilitation of prompt evaluation of reported adverse events and symptoms. Upon receipt from a site of a report of specific adverse events, combinations of symptoms, or symptoms persisting over time that meet pre-specified criteria, the data will be combined with recent laboratory assays and the safety monitor will be notified that there is a report requiring evaluation.

The DCC will also provide monthly reports to the Executive Committee. The Progress Report will include: enrollment and randomization rates, overall and by sex and race; reasons for randomization ineligibility; number of completed follow-up visits; number of completed interim safety bloods; number of blood specimens sent to the central repository; number of dose changes; current distribution of doses; number of patients off drug; reasons for discontinuation; number of unblindings and reasons for the unblindings. The Quality Control Report will include tables on inappropriate randomizations; number of missed visits; reasons for missed visits;

number of visits taking place outside of the designated time windows; and rates of missing data broken down by form. Both the Progress Report and the Quality Control Report will pool participants across treatment groups to maintain the study blind.

The DCC also assumes responsibility for maintenance of blinded treatment assignments. Data files with these assignments will be kept on a secure, password protected server housed in a locked, climate-controlled room with restricted access or on a password protected encrypted laptop. To preserve the integrity of the trial, unblinded DCC staff will not participate in decisions to modify the trial protocol after participants have been randomized. The Steering Committee will obtain statistical input for such decisions from other academic statisticians, blinded to treatment assignment, who also work at Harvard Medical School.

4.18. Data and Safety Monitoring Board

Due to the potential risks to study subjects, the size and multi-site nature of the study, and the fact that this is a Phase III clinical trial, the study will have a formal, and independent, Data and Safety Monitoring Board (DSMB). The DSMB will be constituted by the NHLBI and will include at a minimum members from the following general areas: 1) physicians with specific expertise in the management of patients' cardiovascular disease 2) a biostatistician with specific expertise in the design, analysis, and safety monitoring of multi-center clinical trials 3) a medical ethicist, and 4) a physician with specific expertise in rheumatologic disease. The DSMB will report directly to the NHLBI, and would have the responsibility of monitoring outcome measurements/endpoints, adverse events (AE's), and serious adverse events, and recommending termination of the study if it appeared at any point during the trial that subjects (or a subgroup of subjects) were being placed at undue risk as a result of their participation. Aggregate data on adverse events, stratified by blinded treatment group, will be reviewed on a bimonthly basis by the Chair of the DSMB, and can be brought before the entire DSMB for further review if requested by the Chair.

The DSMB will meet (face-to-face or by teleconference) at designated intervals (semi-annually) to review accumulated data on safety and efficacy, and if appropriate, conduct an interim analysis of the data. Data will be prepared by the Data Coordinating Center (DCC) prior to each meeting of the DSMB. Serious Adverse Events (SAEs) will be initially reviewed with DSMB members blinded to treatment group. If, however, aggregate data suggested a trend toward more frequent SAEs among one treatment group, an unblinded interim analysis would be reviewed by the DSMB. Guidelines for the possible early termination of the study will be formulated by the DSMB and a formal charter agreed upon prior to trial enrollment. The proceedings of each meeting of the DSMB will be recorded in minutes. Any patient-specific protected health information reviewed by the DSMB would be kept completely confidential. Access to the unblinded minutes of the DSMB meetings by Executive/Operations Committee Members, Clinical Site Investigators, or members of the DCC, will be prohibited until after the database for the study has been locked and the study has been unblinded. A formal report will be submitted by the DSMB to the NHLBI, with a recommendation that the study be continued, modified in a manner to enhance subject safety, or terminated.

4.19. Trial Conclusion and Close Out Visits

At the close of the trial, all randomized participants will be asked to return to the local study sites to see a member of the physician's study team. Compliance, side effects, and patient contact information will be collected, and study end points will again be assessed by the local study staff. Therapy with study drug will be discontinued, and the patient's remaining

calendar packs of study drug will be collected. While no observational registry is currently planned, the Clinical Coordinating Center may request that local study sites approach study participants about enrolling in a post-trial observational registry.

To assess the impact of LDM withdrawal on diabetes incidence and glycemic control, participants will have one final laboratory evaluation for ascertainment of HbA1c 3 months after discontinuing study drug therapy.

5.0. DATA ANALYSIS PLAN

5.1. Statistical Analysis

The randomized design and large sample size of CIRT should provide balanced distributions of baseline characteristics between the two treatment groups. Nonetheless, initial analyses will be conducted to identify any chance imbalances in these distributions. In particular, these analyses will form part of the routine monitoring of the trial and will be regularly reported to the DSMB. For continuous and ordinal variables, including age and baseline levels of risk factors including lipid levels, blood pressure, and body mass index, comparisons will use the Wilcoxon rank-sum test. For categorical variables, including sex, race, current and former cigarette smoking, diabetes, greater than 1 prior myocardial infarction, stroke, congestive heart failure, atrial fibrillation, peripheral vascular disease, hypertension, and concomitant therapy with statins, aspirin, clopidogrel, warfarin, beta blockers, ACE inhibitors, and angiotensin receptor blockers, comparisons will use Chi-square tests. These hypothesis tests are intended for data monitoring and quality control, and not to determine which baseline covariates to include in efficacy analyses⁵⁰.

The primary endpoint of the trial is the time from randomization to the first occurrence of any component of the clinical composite endpoint including myocardial infarction, stroke and cardiovascular death. The primary analysis of the trial will use a likelihood ratio test based on a proportional hazards model stratified on time since qualifying event (≥ 6 months vs. < 6 months), type of event (myocardial infarction vs. multivessel coronary disease), and presence of either diabetes or metabolic syndrome to test the null hypothesis of no association between assignment to active methotrexate and the rate of the primary endpoint. All analyses will classify patients according to their randomized treatment assignment, i.e. according to the intention to treat principle, and will base evaluation of statistical significance on a two-sided test with level 0.05. Secondary analyses will further stratify on study site, although these analyses will likely be less efficient because of sparse strata that will arise because of small numbers of participants from some sites. The estimated relative hazard in the methotrexate group compared to the placebo group with an accompanying 95% confidence interval will quantify the treatment effect⁵¹. If this relative hazard is less than 1, then $100 \times (1 - \text{estimated relative hazard})$ will be defined as the percent reduction in hazard associated with methotrexate treatment.

Rates of occurrence of the primary endpoint will be defined as the total number of subjects who have this event in a treatment group per 100 person-years of follow-up, counting all time from randomization until the first of the event, death, end of trial, or withdrawal of consent. Estimates of the probability of the primary endpoint by time after randomization within treatment groups will be based on the method of Kaplan and Meier⁵². We will also use the proportional hazards model to control for baseline factors that might influence the rate of the primary endpoint (e.g. age, race, gender, baseline comorbidities, and concomitant medications), as control for these variables may yield more efficient estimates of relative treatment effects⁵³. If Kaplan-Meier plots of event free survival by study time, or related plots of $\log(-\log)(\text{survival})$, indicate violations of the proportional hazards assumption, or a formal test of trend in the scaled Schoenfeld residuals indicates such a violation, then weighted log-rank tests will be used

according to strategies described by Pecková and Fleming⁵⁴. However, even in the presence of an apparent violation of the proportional hazards assumption, the primary analysis described above gives a valid (although perhaps not optimal) test of the main trial hypothesis and will remain the primary analytic strategy, with these weighted log-rank tests serving as sensitivity analyses.

5.2. Sample Size and Power

Sample size and power for CIRT have been estimated under several alternative assumptions about the rate of the primary endpoint in the placebo group and the likely reduction in this rate among those in the methotrexate group. All estimates are based on a two-sided log-rank test comparing the time to recurrence between two treatment groups at the 0.05 significance level. These estimates use the approach of Lachin and Foulkes under the assumption of a uniform hazard and to account for attrition due to drop-out⁵⁵. The following assumptions have been made:

- (a) Based on previous trials in individuals with a prior myocardial infarction or multivessel coronary disease, and considering the increased rate of major cardiovascular events associated with either diabetes or metabolic syndrome, it is anticipated that annual event rates between 3.25 and 4.0 per 100 person-years in the placebo group.
- (b) A clinically meaningful reduction in the rate of the primary endpoint is assumed to be in the range from 25% to 35%.
- (c) The recruitment period will be split into a ramp-up period, followed by steady-state randomization. Each randomized patient will be asked to continue blinded treatment until study completion.
- (d) As these patients have strong affiliations with their treatment centers and will have been tested in a run-in period, low rates of loss to follow-up are anticipated. Power calculations assume a 5% annual rate of loss to follow-up.

Under these assumptions Lachin and Foulkes show that the power of the trial with N total randomized subjects in the methotrexate and placebo groups combined is

$$Power = \Phi^{-1} \left(\sqrt{N} (\lambda_c - \lambda_e - 3.92 \sqrt{\Psi(\bar{\lambda})}) / (2\Psi(\lambda_e) + 2\Psi(\lambda_c))^{1/2} \right)$$

where Φ is the standard normal distribution function,

$$\Psi(\lambda) = \lambda(\lambda + .05) / (1 - [\exp(-2(\lambda + .05)) - \exp(-4(\lambda + .05))] / (2(\lambda + .05))),$$

λ_c is the incidence rate in the methotrexate group,

λ_e is the incidence rate in the placebo group

$$\bar{\lambda} = .5\lambda_e + .5\lambda_c$$

follow-up for uncensored subjects without events ranges from 2 to 4 years.

Table 4 shows the power of CIRT to detect alternative relative hazard rates in an active treatment group with 3500 patients compared to 3500 patients who receive placebo. The trial has good power (>90%) to detect hazard reductions of 25% or greater for the range of reasonable event rates in the placebo group, and power of 95% or greater to detect a reduction of 25% or greater if event rates in the placebo group are 4.0 per 100 person-years or greater.

These power calculations are based on intention to treat analyses of observed event rates. As such, they incorporate the effects of non-compliance. We estimate, based on experience observed in other trials, that, in addition to those who drop out, 10% of the methotrexate group will discontinue active therapy but that none of the placebo group will initiate open-label therapy (drop-in). The impact of non-compliance on power can be evaluated from interpolation using Table 4. For example, if the true rate of major cardiovascular events in persons meeting eligibility criteria but not on methotrexate is 3.5 per 100-person years, and fully

compliant methotrexate reduces this rate by 30%, we estimate a rate of the primary endpoint of 2.555 per 100 person-years in the methotrexate group and 3.5 per 100 person-years in the placebo group. This would correspond to an observed 27% reduction in the active treatment group relative to placebo with the above non-compliance and drop-in rates. The proposed trial would thus have power above 90% to detect such a true effect. However, we base primary

Table 4. Power of CIRT for alternative event rates and effect sizes in this proposal

Relative Rate	Rate of Major Cardiovascular Events in the Placebo Group (per 100 person-years)			
	3.25	3.5	3.75	4.0
.75	91%	93%	94%	95%
.7	98%	99%	99%	99%
.65	>99%	>99%	>99%	>99%

evaluation of study power on observed event rates and intention to treat analyses, as summarized in Table 4.

Another perspective on sample size estimation based on the above formulation of enrollment indicates that, regardless of the rate of major cardiovascular events in the placebo group, the trial must accrue 514 total confirmed major cardiovascular events in order to have 90% power to detect a 25% reduction in this rate, based on a two-sided test with $\alpha=0.05$. Given a conservative interim monitoring plan such as that described below, then the approach of Reboussin et al⁵⁶ indicates that sample size needs to be increased by 1.9% to maintain 90% power in the presence of monitoring. We therefore stipulate that the trial will require accrual of 530 total primary events. With respect to the above assumptions on accrual and drop out, and the range of event rates in the placebo group shown in the above table, the proposed trial with 7,000 randomized subjects would be expected to accrue between 529 endpoints (placebo event rate=0.0325/100 person-years) and 645 endpoints (placebo event rate=0.040/100 person-years) under the assumption of a 25% reduction in hazard associated with methotrexate.

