1.0. TRIAL OVERVIEW

While inflammation contributes crucially to atherothrombosis, it is unknown whether inhibition of inflammation per se will lower vascular event rates. The primary aim of the **Cardiovascular Inflammation Reduction Trial (CIRT)** is to directly test the inflammatory hypothesis of atherothrombosis by evaluating whether or not low-dose methotrexate (LDM) will reduce rates of myocardial infarction, stroke, and cardiovascular death among stable coronary artery disease patients with type 2 diabetes or metabolic syndrome, conditions associated with an enhanced pro-inflammatory response. CIRT is a randomized, double-blind, placebo-controlled, multi-center, event-driven trial that will randomize 7,000 men and women from the United States and Canada. Following a five- to six-week open-label run-in (maximum 8 weeks), eligible participants who have either suffered documented myocardial infarction in the past or have angiographically demonstrated multivessel coronary artery disease in the past will be randomly allocated over a three to four year period to usual care plus placebo or usual care plus LDM. The target methotrexate dose among those allocated to active therapy is 15 to 20 mg po per week, a dose within the range of that commonly used for the treatment of rheumatoid arthritis. All study participants will additionally receive 1.0 mg oral folate to be taken daily six days per week. LDM complications will be minimized through education programs for all investigators and coordinators, through enhanced communication with study participants, by limiting enrollment to those with no evidence of malignancy, hepatitis, renal dysfunction, chronic infection, pulmonary disease, or other risk factors for toxicity; by conducting an initial 5- to 6-week active-therapy run-in (maximum 8 weeks) designed to eliminate individuals who are either intolerant of or unable to adhere to treatment before randomization; and through regular monitoring of liver function and hematologic indices using a centralized methodology designed to ensure participant safety, allow for dose adjustments while maintaining the study blind, and provide an efficient method to address issues of compliance and follow-up on a cost-effective centralized basis. The primary trial endpoint is the rate of myocardial infarction, stroke, or cardiovascular death. Secondary and tertiary endpoints include all-cause mortality, coronary revascularization, incident congestive heart failure, incident peripheral artery disease, incident venous thrombosis, clinically significant aortic stenosis, incident atrial fibrillation, incident diabetes among those with metabolic syndrome but not diabetes at study entry, and hemoglobin A1c (HbA1c) control among those with diabetes at study entry. The trial is event driven such that in the absence of extreme effects, the trial will conclude after accrual of at least 530 primary endpoints, an effect estimated to provide 90 percent power to detect a 25 percent relative risk reduction. The potential clinical impact of CIRT is broad as it has sufficient power to directly address core issues in the inflammatory hypothesis of atherothrombosis, and thus, if successful, will open major new directions for cardiovascular treatment.

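### Do the differing descriptions of recruitment and follow-up undermine the power table and the 529-645 event projection?

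*Combined protocol and SAP*

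**What the plan says.** Protocol 5.2 lists its assumptions, among them (c): "The recruitment period will be split into a ramp-up period, followed by steady-state randomization". No length is given for either phase, and each patient continues blinded treatment until the study ends. The formula follows, introduced by "Under these assumptions Lachin and Foulkes show that the power of the trial with N total randomized subjects". Its variance term contains exp(-2(λ+.05)) - exp(-4(λ+.05)) divided by 2(λ+.05), and the section closes the definition by saying that "follow-up for uncensored subjects without events ranges from 2 to 4 years".

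From this the section claims "good power (>90%) to detect hazard reductions of 25% or greater for the range of reasonable event rates in the placebo group". It then says, "With respect to the above assumptions on accrual and drop out", that 7,000 participants "would be expected to accrue between 529 endpoints" at the lowest placebo rate and 645 at the highest. SAP 1.3 repeats assumption (c), the formula, the follow-up range and the projection.

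Two other places mention a period. Overview 1.0 says that participants "will be randomly allocated over a three to four year period to usual care plus placebo or usual care plus LDM". SAP 1.2 describes the same design without a time phrase on allocation and says instead that subjects are followed for three to four years. Overview 1.0 also gives the stopping rule: "the trial will conclude after accrual of at least 530 primary endpoints".

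**The concern.** With a common close, the spread of follow-up equals the length of recruitment. A range of 2 to 4 years therefore means two years of recruitment. Three statements do not fit that:

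- Assumption (c) has a ramp-up, and a uniform-entry formula has no term for one, although it is presented as following from the listed assumptions.
- Read literally, overview 1.0 gives three to four years of recruitment, which would spread follow-up over three to four years.
- Read literally as a minimum and a maximum, SAP 1.2 gives follow-up of 3 to 4 years, not 2 to 4.

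The lowest-rate projection of 529 has no slack against the target of 530. A less favourable accrual pattern would then mean fewer than 530 events by year 4, power just under the claimed 90% at that date, and a longer trial than a reader of 5.2 would expect.

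**Working it through.** **Inputs.** Protocol 5.2 and SAP 1.3 give N = 7,000 (3,500 per group), placebo rate λc of 0.0325 to 0.040 per person-year, loss of 0.05 per year, two-sided alpha 0.05 and, for the projection, hazard ratio 0.75, so λe = 0.75λc. I use λc for placebo, as in SAP 1.3; the protocol prints the two labels the other way round. The printed Φ⁻¹ is read as Φ, and √N is applied to the rate difference only. Taken literally the argument is about -160, so the table was evidently not computed that way.

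**Formulas**, for uniform entry over R years and close at T:

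- P(λ) = λ/(λ+.05) × {1 - [exp(-(λ+.05)(T-R)) - exp(-(λ+.05)T)] / [R(λ+.05)]}
- Events = 3,500 × [P(λc) + P(λe)]
- Ψ(λ) = λ²/P(λ), which at R = 2, T = 4 is the printed Ψ
- Power = Φ{[√N(λc-λe) - 3.92√Ψ(λ̄)] / √[2Ψ(λe)+2Ψ(λc)]}

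**Reproducing the plan (R = 2, T = 4, λc = 0.0325, λe = 0.024375).**

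- P(λc) = 0.08602 and P(λe) = 0.06530, so events = 3,500 × 0.15132 = 529.6.
- √N(λc-λe) = 83.666 × 0.008125 = 0.6798.
- Ψ(λ̄) = 0.010679, so 3.92√Ψ(λ̄) = 0.4051.
- √[2(0.009099) + 2(0.012279)] = 0.2068.
- (0.6798 - 0.4051)/0.2068 = 1.328, and Φ(1.328) = 90.8%.

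Across placebo rates 3.25, 3.5, 3.75 and 4.0 this gives 529.6, 568.5, 607.1 and 645.4 events, and power 90.8%, 92.6%, 94.1% and 95.3%. The plan prints 529 to 645 and 91%, 93%, 94%, 95%.

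**Other readings.** The ramp is assumed linear and its lengths are assumptions, since none is stated. Where T is not printed it is also an assumption. Ranges run from placebo rate 3.25 to 4.0.

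| Pattern | Events | Power |
|---|---|---|
| As printed: R = 2, T = 4 | 530-645 | 90.8-95.3% |
| 0.25-year ramp inside R = 2, T = 4 | 520-634 | 90.3-94.9% |
| 0.5-year ramp inside R = 2, T = 4 | 511-623 | 89.8-94.6% |
| 1-year ramp inside R = 2, T = 4 | 495-604 | 88.9-94.0% |
| 0.5-year ramp, then 2 years steady, T = 4.5 | 549-669 | 91.8-95.9% |
| 1-year ramp, then 2 years steady, T = 5 | 570-694 | 92.7-96.4% |
| Follow-up 3 to 4 years: R = 1, T = 4 | 608-740 | 94.1-97.3% |
| Uniform R = 3, T = 4.52 | 530-646 | 90.8-95.3% |
| Uniform R = 4, T = 5.04 | 530-645 | 90.8-95.2% |

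**Calendar time to 530 events**, at placebo rates 3.25 and 4.0:

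- R = 2, no ramp: 4.00 and 3.41 years
- R = 2, 0.5-year ramp inside: 4.12 and 3.52
- R = 2, 1-year ramp inside: 4.22 and 3.62
- R = 3, no ramp: 4.52 and 3.92
- R = 4, no ramp: 5.04 and 4.45

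**Power at the stopping point.** By Schoenfeld's formula, Φ(0.2877 × √(530/4) - 1.96) = Φ(1.351) = 91.2%, before interim looks. Neither the accrual pattern nor the closing date enters.

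**The case for a change.** The strongest case for a change is that assumption (c) stands in the same section as the formula said to follow from it, so the conflict is not just between distant parts of the documents. With the printed 2-to-4-year range kept and a half-year ramp inside it, power at the lowest rate is 89.8%, so the claim of more than 90% across the whole range fails at its lower end. A funder also cannot tell whether 530 events are expected at about 4.0, 4.5 or 5.0 years.

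The omission of the ramp is real, and the phrases do not match. The rest is weaker than it looks:

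- The 89.8% belongs to a trial that closes at 4 years with 511 events. No section fixes that close; the trial runs to at least 530.
- The direction is not determined. Assumption (c) puts the ramp before the steady phase. If two full years of steady accrual follow and the 2-year minimum is kept, events and power rise, although maximum follow-up then exceeds 4 years.
- The overview and SAP phrases are loose. SAP 1.2 moves the same period from allocation to follow-up, which suggests one phrase misplaced. The 608-740 figure needs all 7,000 participants recruited within one year, which no section says.
- The widest differences in duration come from the allocation reading of overview 1.0. Neither 5.2 nor SAP 1.3 states a planned duration that those figures would contradict.

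**Conclusion.** No change to the plan follows. Uniform entry over two years is an ordinary simplification for a planning calculation. For those inputs the power table and the 529-645 projection are correct, and no printed figure is shown to be wrong in a definite direction. What remains is loose wording about recruitment and follow-up, which those running the trial resolve by counting events.

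If the 2-to-4-year range is kept, ramps of 0.25 to 1 year cost about 10 to 35 events and 0.5 to 1.9 percentage points of power at the lowest rate. With the trial run to its target, a 1-year ramp costs 0.22 years, or 0.22 × 12 = 2.6 months. These figures rest on an assumed linear ramp, constant hazards, 5% annual loss and a hazard ratio of 0.75. Power of 91.2% at 530 events depends only on the hazard ratio, proportional hazards and equal allocation. The sample size, event target, alpha, boundaries and primary analysis stand on any of these readings. A sentence calling the entry pattern an approximation would be a courtesy to the reader; the trial would be conducted and analysed in the same way without it.
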